Upon completion of the 60-minute observations, resumption of normal medications is permitted for the remainder of the day (the patient may use the inhaled study drug 4 more times at home after he/she leaves the clinic on that day if needed for OFF episodes). The next visit will be scheduled. Clinic staff will arrange to speak with patients by telephone 1 to 3 days after TV/OV1 to monitor for AEs and to address any potential concerns or challenges with the inhaler systems or Inhaled Dosing Log. Additionally, clinic staff will arrange to speak with patients by telephone 2 weeks (\pm 3 days) before each visit for TV2, TV3, TV4, TV5, and TV6 to address any concerns or challenges with the inhaler systems, PD Diary, or Inhaled Dosing Log, to monitor for any AEs, to confirm the DLco assessment has been done/scheduled (prior to TV3, TV4, TV5, and TV6), to confirm the next study visit, to ask the patients how many empty study drug kits will be returned at the next visit, and also to remind patients of the study procedures

required prior to the next scheduled study visit (including completion of the PD Diary and Inhaled Dosing Log).

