11.1.8. Adverse Events

An AE is any symptom, physical sign, syndrome, or disease that either emerges during the study or, if present at the start of the study, worsens during the study, regardless of the suspected cause of the event. Changes in conditions present at screening and new symptoms, physical signs, syndromes, or diseases should be noted on the AE page of the eCRF during the study. Any AEs reported prior to the first study treatment (or TV/OV1) will be considered baseline AEs, and AEs reported from first treatment (or TV/OV1) will be considered treatment-emergent adverse events (TEAEs).

AEs may be volunteered spontaneously by the patient, discovered as a result of general questioning by the study staff, or determined by physical examination. At each visit, the patient will be asked, “Have you experienced any problems since your last visit?” All AEs will be recorded on the eCRF. For all AEs, the investigator must pursue and obtain information adequate both to determine the outcome of the AE and to assess whether it meets the criteria for classification as a serious AE requiring immediate notification. Follow-up of the AE, even after the date of therapy discontinuation, is required if the AE persists until the event resolves or stabilizes at a level acceptable to the investigator.

In order to avoid vague, ambiguous, or colloquial expressions, all AEs should be recorded in standard medical terminology rather than the patient’s own words. Each AE will also be described in terms of duration, frequency, intensity, association with the study medication, assessment of possible causes, actions taken, and outcome, using choices given on the eCRF. Specific guidelines for classifying AEs by intensity and relationship to study medication are given in [Table 3](#) and [Table 4](#), respectively.

Table 3 Classification of Adverse Events by Intensity

MILD: An event that is easily tolerated by the patient, causing minimal discomfort and not interfering with everyday activities.

MODERATE: An event that is sufficiently discomforting to interfere with normal everyday activities.

SEVERE: An event that prevents normal everyday activities.

Table 4 Classification of Adverse Events by Relationship to Study Medication

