11.1.9. Serious Adverse Events

A serious adverse event (SAE) is defined as any AE that meets 1 or more of the following criteria:

- The event results in death.
- The event is life-threatening.
- The event is permanently disabling (incapacitating or interfering with the ability to resume usual life patterns).
- The event results in unplanned inpatient hospitalization or prolongation of existing hospitalization.
- The event is a congenital anomaly.
- The event requires medical intervention of any kind in order to prevent any of the aforementioned outcomes.

A serious AE is not necessarily severe; for example, an overnight hospitalization for a diagnostic procedure must be reported as a serious AE even though the occurrence is not medically serious. By the same token, a severe AE is not necessarily serious: for example, nausea of several hours' duration may be rated as severe but may not be considered serious.

An SAE occurring during the study or within 4 weeks of stopping the treatment must be reported to the [REDACTED] and will be communicated to the Sponsor. **Any such SAE due to any cause, whether or not related to the study medication, must be reported within**

24 hours of occurrence or when the investigator becomes aware of the event. Notification can be made using the following fax or email address for the [REDACTED]:

[REDACTED]

The event must also be recorded on the standard AE eCRF. Preliminary reports of SAEs must be followed by detailed descriptions later on, including clear and anonymized photocopies of hospital case reports, consultant reports, autopsy reports, and other documents when requested and applicable. SAE reports must be made whether or not the investigator considers the event to be related to the investigational drug.

Appropriate remedial measures should be taken to treat the SAE, and the response should be recorded. Clinical, laboratory, and diagnostic measures should be employed as needed in order to determine the etiology of the problem. The investigator must report all additional follow-up evaluations to the [REDACTED] within 10 calendar days. All SAEs will be followed until the investigator and Sponsor agree the event is satisfactorily resolved.

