12.2. Study Populations

All patients who are enrolled in CVT-301-005 and receive at least 1 dose of CVT-301 will be included in the safety population. The patients in the observational cohort will be included in the analyses if they provide any data after TV/OV1.

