12.5. Safety Analysis

The disposition of the patients will be summarized by tabulating the number of screened, randomized, completed, and discontinued patients. The reasons for premature discontinuations will be tabulated.

The extent of exposure to study treatment will be summarized for the patients who received CVT-301 treatment. The time period between TV/OV1 and TV/OV6 (or Early Withdrawal Visit) will be used as the measure of extent of exposure for the patients randomized to the observational cohort. Adverse events will be tabulated by treatment group according to the Medical Dictionary for Regulatory Activities (MedDRA). Study-emergent and treatment-emergent adverse events (TEAEs) will be summarized by body system and preferred term. For patients in the observational cohort, the AEs collected between TV/OV1 and TV/OV6 (or Early Withdrawal Visit) will be considered as TEAEs. Furthermore, the time of onset of the TEAEs will be summarized.

For vital signs, ECG parameters, spirometry measurements, and DLco, the changes from pre-dose to post-dose assessments of the corresponding day will be calculated and described using descriptive statistics. For spirometry, DLco, and safety laboratory variables, the differences in pre-dose values between the study days will be described. Furthermore, the changes in the spirometry values and difference between the groups will be estimated using a Mixed Model for Repeated Measurements (MMRM) similar to the one used for the efficacy variables. The proportion of patients with abnormal spirometry values will be tabulated using different criteria for the threshold (e.g., at least 10% or 20% change from baseline at any single visit, at least 10% or 20% change from baseline on at least 2 consecutive visits). The proportions of patients meeting ATS quality criteria (and also for those 'rejected') will be summarized. All spirometry analyses will be performed both for all patients regardless of the ATS quality criteria and separately excluding the assessments not meeting the ATS quality criteria.

At least the following variables will be analyzed:

- Vital signs: standard and orthostatic systolic and diastolic BP and HR.
- ECG: HR, PR, QRS, QT and RR intervals, QTcB (Bazett's correction formula calculated as $QT/RR^{1/2}$) and QTcF (Fridericia's correction formula calculated as

QT/RR^{1/3}). ECG parameter values or parameter changes of potential clinical concern will be tabulated.

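### Controls enter the AE analyses, and leave the TEAE window, under different rules from CVT-301 patients, which puts a small, avoidable artefact in the descriptive by-group AE tables

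*Protocol*

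**What the plan says.** **Entry.** Protocol Section 12.2 sets one rule per arm. For CVT-301: "All patients who are enrolled in CVT-301-005 and receive at least 1 dose of CVT-301 will be included in the safety population". For controls: "The patients in the observational cohort will be included in the analyses if they provide any data after TV/OV1". The Synopsis repeats both rules. Section 10.3 places the first dose in the clinic at TV1, so a CVT-301 patient qualifies at that visit and needs no later data.

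**Window.** Section 11.1.8 gives the general definition: "AEs reported from first treatment (or TV/OV1) will be considered treatment-emergent adverse events (TEAEs"). The start is aligned between the arms and no end is given. Section 12.5, again repeated in the Synopsis, adds an end for one arm: "For patients in the observational cohort, the AEs collected between TV/OV1 and TV/OV6 (or Early Withdrawal Visit) will be considered as TEAEs". No matching sentence exists for CVT-301 patients.

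**After visit 6.** Section 11.1.9 extends serious-event reporting: "An SAE occurring during the study or within 4 weeks of stopping the treatment must be reported". Patients in both arms are due at a pulmonary laboratory 4 to 5 weeks after visit 6 (Section 7) or after an Early Withdrawal Visit (Section 10.3.9).

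**Use.** Section 12.5 tabulates AEs by treatment group. AE reports are part of a secondary safety objective in Section 6.

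**The concern.** The control arm is randomised, and readers will compare the two AE columns whether or not a formal comparison is planned. The columns should therefore differ only in what happened to the patients. Here they also differ by rule in two ways.

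- The control entry rule conditions on what happens after baseline. A control who is silent after OV1 is not counted, while a CVT-301 patient who is silent after the first dose is counted as event-free. This raises the control proportion.
- The TEAE window is closed for controls and, in this document, open for CVT-301 patients. The same event a few weeks after visit 6 could be a TEAE in one arm and not in the other. This raises the CVT-301 proportion.

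The two effects push in opposite directions, so the protocol gives no basis for saying which arm is favoured overall. What is at stake is how cleanly the descriptive safety tables can be read. The spirometry comparison and its power statement are not affected.

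**Working it through.** **1. Denominators.** Section 12.1 plans 250 CVT-301 and 115 control patients with about 25% drop-out. 250 × 0.75 = 187.5 and 115 × 0.75 = 86.25, which reproduces the stated 188 and 86 completers. The point does not rest on these figures; they only confirm the enrolment numbers used below. The protocol gives no AE incidence, so every incidence and every count of lost controls below is an assumption.

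**2. Who is lost under the control entry rule.** Section 8.3 asks that every effort be made to complete the visit 6 assessments in patients who discontinue, and Section 10.3.9 does the same through the Early Withdrawal Visit. Section 10.3.1 has controls telephoned about AEs 2 weeks before OV2. A control reached by any of these has presumably supplied later data. The rule therefore removes only controls with no contact at all after OV1.

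**3. Size of the entry effect.** If k of 115 controls are lost and none had a counted AE, the control proportion is multiplied by 115/(115 − k). With an assumed 20% (23 of 115):

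| k lost | factor | proportion shown |
|---|---|---|
| 2 | 115/113 = 1.018 | 23/113 = 20.4% |
| 6 | 115/109 = 1.055 | 23/109 = 21.1% |
| 12 | 115/103 = 1.117 | 23/103 = 22.3% |

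**4. What is collected after visit 6.** The post-visit columns of Appendices 14 and 15 list the DLco assessment and no AE monitoring. The only explicit tail is the 4 weeks in Section 11.1.9, and it covers SAEs.

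**5. Size of the window effect.** With a constant hazard and incidence p at 52 weeks, incidence over 52 + t weeks is 1 − (1 − p)^((52 + t)/52).

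- SAE tail, t = 4: the window is 56/52 = 1.077 times as long. An assumed 1% becomes 1.08%, and 5% becomes 5.4%.
- For a patient who withdraws at week 12, a 4-week tail gives 16/12 = 1.33 times the window, so the relative effect is larger in early leavers.
- Ceiling, only if all AEs were also captured up to the pulmonary visit (t = 4 to 5): 57/52 = 1.096 at most. An assumed 20% becomes 21.4% to 21.7%, and 50% becomes 52.6% to 53.2%. Step 4 shows no scheduled procedure that would collect these events.

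**6. Against sampling error.** At 20% in both arms the 95% half-width for a difference is 1.96 × √(0.16 × (1/250 + 1/115)) = 1.96 × 0.0451 = 8.8 percentage points. The entry effect in step 3 is 0.4 to 2.3 points.

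**The case against.** The strongest reply is that a TEAE end date is ordinary SAP detail. The introduction to Section 12 says the SAP gives the technical description and supersedes the protocol where they differ. That is right as far as it goes: the SAP is not at hand and may set a CVT-301 end date. What remains is that the protocol itself chose to fix the end for one arm, and fixed unequal entry rules. Those are stated rules, not omissions.

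The reply also has force on size. The CVT-301 arm has a filter of its own, since a patient randomised but never dosed is excluded. Section 12 has all data listed, and Section 12.5 summarises time to TEAE onset and defines control exposure time. Few controls are likely to be lost.

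A reader might be tempted by four stronger readings that the documents do not support.

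- *Every control who leaves soon after OV1 is dropped.* An Early Withdrawal Visit or a telephone report after OV1 would presumably satisfy the rule.
- *CVT-301 patients are observed for AEs for 56 to 57 weeks against 52.* Nothing scheduled after visit 6 collects AEs in either arm, and the explicit tail is for SAEs.
- *The extra CVT-301 telephone call, "by telephone 1 to 3 days after TV/OV1 to monitor for AEs", is a flaw of the same kind.* It follows a first dose that controls do not receive, every patient is asked at each visit about problems since the last one (Section 11.1.8), and some unequal ascertainment is inherent in an open-label design without placebo.
- *The AE difference cannot be read as a drug effect.* No AE difference is planned: in Section 6 the between-group estimation objective concerns pulmonary measures, and the AE objective is to characterise the effects of CVT-301.

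**Conclusion.** The point holds as a mismatch of definitions in the descriptive AE tables. Controls with no contact after OV1 fall out of the denominator while CVT-301 patients in the same position stay in. Events after visit 6, in practice chiefly SAEs, can be TEAEs in the CVT-301 arm only.

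The effect is probably small. It is about 0.4 to 2.3 points on the control proportion if 2 to 12 of 115 event-free controls are lost at an assumed 20% incidence, and about 0.4 points on an assumed 5% SAE incidence with a 4-week tail. These figures assume a constant hazard and that lost controls had no counted AE; the protocol supplies neither the incidences nor the losses. The two effects oppose each other and the net direction is unknown. The mismatch is worth correcting because it is unnecessary and nearly free to remove, not because it undermines the safety conclusions.

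**What to change.** - **Section 12.2 and the matching Synopsis text:** include in the safety analyses every randomised control who attends OV1, as the counterpart of dosing at TV1. These patients are already identifiable, because Section 8.3 requires an end-of-study page for each control who enters that visit. Analyses that need a post-baseline value, such as change in spirometry, are unaffected.
- **Section 12.5 and the matching Synopsis text:** for the by-group tables, apply the same TEAE window end to both arms, for example TV/OV6 or Early Withdrawal, and list later events separately for both arms. If the SAP already sets an end for CVT-301 patients, the control end should be set to match.

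The cost is wording only and no new data are needed. A few controls with little follow-up join the denominator, and any CVT-301 events after visit 6 move from the main table to the separate listing.

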12.3. Definition of Baseline

In all statistical analyses of the CVT-301 treatment group, the visit at which the CVT-301 treatment was initiated will be used as the baseline. However, for all patients who were included in the CVT-301-002 or CVT-301-003 studies, TV/OV1 of the CVT-301-005 study will be used as baseline. For the observational cohort, the assessments at TV/OV1 will be used as baseline.

12.4. Background and Demographic Characteristics

Demographics and baseline characteristics will be summarized descriptively for patients treated with CVT-301 and for the patients in the observational cohort. In addition to the total CVT-301 group, the data from the CVT-301 naïve patients who are enrolled in this study and from the patients who were previously enrolled in the CVT-301-002 or CVT-301-003 studies will be summarized separately. At least the following variables will be summarized:

- Demographics (age, gender, race, height, weight)
- Smoking history (current, former, never: pack-years for current and former smoker)
- History of PD (UK Brain Bank criteria, time since diagnosis of PD, duration of LD treatment)

- LD treatment at baseline (total daily dose, dosing frequency, decarboxylase inhibitor [CD or benserazide], use of standard/quick/controlled release LD, use of COMT inhibitor)
- Other antiparkinsonian treatment at baseline (use of dopamine agonists, MAO-B inhibitors, anticholinergics, amantadine, or other treatment)
- Disease severity (modified Hoehn and Yahr stage [in the ON state], UPDRS Part 3 at screening)
- Cognitive status (MMSE)
- Average daily number of OFF episodes experienced (determined from Screening ON/OFF Episodes and Treatment Log).

12.5. Safety Analysis

The disposition of the patients will be summarized by tabulating the number of screened, randomized, completed, and discontinued patients. The reasons for premature discontinuations will be tabulated.

The extent of exposure to study treatment will be summarized for the patients who received CVT-301 treatment. The time period between TV/OV1 and TV/OV6 (or Early Withdrawal Visit) will be used as the measure of extent of exposure for the patients randomized to the observational cohort. Adverse events will be tabulated by treatment group according to the Medical Dictionary for Regulatory Activities (MedDRA). Study-emergent and treatment-emergent adverse events (TEAEs) will be summarized by body system and preferred term. For patients in the observational cohort, the AEs collected between TV/OV1 and TV/OV6 (or Early Withdrawal Visit) will be considered as TEAEs. Furthermore, the time of onset of the TEAEs will be summarized.

For vital signs, ECG parameters, spirometry measurements, and DLco, the changes from pre-dose to post-dose assessments of the corresponding day will be calculated and described using descriptive statistics. For spirometry, DLco, and safety laboratory variables, the differences in pre-dose values between the study days will be described. Furthermore, the changes in the spirometry values and difference between the groups will be estimated using a Mixed Model for Repeated Measurements (MMRM) similar to the one used for the efficacy variables. The proportion of patients with abnormal spirometry values will be tabulated using different criteria for the threshold (e.g., at least 10% or 20% change from baseline at any single visit, at least 10% or 20% change from baseline on at least 2 consecutive visits). The proportions of patients meeting ATS quality criteria (and also for those 'rejected') will be summarized. All spirometry analyses will be performed both for all patients regardless of the ATS quality criteria and separately excluding the assessments not meeting the ATS quality criteria.

At least the following variables will be analyzed:

- Vital signs: standard and orthostatic systolic and diastolic BP and HR.
- ECG: HR, PR, QRS, QT and RR intervals, QTcB (Bazett's correction formula calculated as $QT/RR^{1/2}$) and QTcF (Fridericia's correction formula calculated as

QT/RR^{1/3}). ECG parameter values or parameter changes of potential clinical concern will be tabulated.

- Spirometry: FEV1, FVC, and the FEV1/FVC ratio during specified treatment visits and over the course of the study will be evaluated. The number and proportion of patients with pre-specified changes in spirometry parameters will be tabulated.

Changes from baseline to follow-up in the rating scales for assessing suicidality, somnolence, and impulse control disorders will be summarized descriptively.

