CVT-301-treated patients will be followed in the clinic for the following efficacy measures: serial assessments of UPDRS Part 3 motor score following treatment in the clinic, the occurrence and severity of dyskinesia following treatment in the clinic, the occurrence of ON states during the post-treatment period, the 39-Item Parkinson's Disease Questionnaire (PDQ-39), the Patient Global Impression of Change (PGI-C) rating scale, the Schwab and England (S&E) Activities of Daily Living (ADL) score; UPDRS Part 2 score, and UPDRS Part 4 (Questions 32-35 and 36-39) score. In addition, the total daily ON time without dyskinesia, total daily ON time with troublesome dyskinesia, total daily ON time with non-troublesome dyskinesia, and total daily OFF time will be evaluated in the CVT-301-treated patients based on the PD Diary, which will be completed for the 3 consecutive days prior to SV2, TV/OV1, TV/OV2, TV/OV3, TV/OV4, TV/OV5, and TV/OV6.

All patients, regardless of treatment assignment, will undergo the safety assessments. Patient safety will be evaluated using adverse event (AE) reports, physical examination, vital signs (blood pressure [BP], heart rate [HR], and respiratory rate [RR]), clinical laboratory tests, 12-lead electrocardiograms (ECGs), spirometry, carbon monoxide diffusing capacity (DLco) maneuver, the Parkinson's Disease Impulsive-Compulsive Disorders Questionnaire (QUIP), the Epworth Sleepiness Scale, and the Columbia-Suicide Severity Rating Scale (C-SSRS).

The use of a randomized observational cohort in this study is to permit long-term contemporaneous temporal comparison to CVT-301-treated patients to describe any potential effects of CVT-301 with respect to lung function measurements. These control patients, who are eligible to use any approved treatments to manage their PD motor symptoms, represent a randomized study population that remains naïve to inhalation treatment (to avoid potential confounding interpretation of lung function data) for their PD which is required to ascertain the underlying variability in spirometry and DLco endpoints. Only a limited number of efficacy assessments will be evaluated in the patients randomized to the observational cohort. Selected efficacy measures to assess effects of CVT-301 will be evaluated in the open-label CVT-301-treated patients who use CVT-301 inhalation as a treatment of OFF symptoms.

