6. STUDY OBJECTIVES

Primary Objective

- To characterize the pulmonary safety, as assessed by spirometry (forced expiratory volume in 1 second [FEV1], forced vital capacity [FVC], and FEV1/ FVC ratio), over a 12-month period within the CVT-301-treated patients.

Secondary Objectives

- To characterize the pulmonary safety, as assessed by spirometry (FEV1, FVC, and FEV1/FVC ratio), over a 12-month period in the observational ('standard of care') cohort.
- To estimate the difference between the CVT-301-patients and the observational cohort on measures of pulmonary safety.
- To characterize the effects of CVT-301 on safety over a 12-month period: safety will be assessed by AE reports, physical examination, standard and orthostatic vital signs (BP, HR, and RR), clinical laboratory tests, 12-lead ECGs, QUIP, the Epworth Sleepiness Scale, and the C-SSRS.
- To evaluate the effect of CVT-301 on mean change from baseline in the UPDRS Part 4 measures of motor fluctuations (dyskinesias [Q32-35] and wearing off [Q36-39]) measured pre-dose at 6 and 12 months after the initiation of CVT-301 treatment.
- To characterize the occurrence and severity of examiner-rated dyskinesia following treatment of patients experiencing an OFF episode in the clinic over a 12-month period.
- To describe the effects of CVT-301 on DLco over a 12-month period.

Exploratory Efficacy Objectives

- Change from pre-dose in UPDRS Part 3 motor score at 10, 20, 30, and 60 minutes following treatment of patients experiencing an OFF episode.
- Time curves of the UPDRS response at 10, 20, 30 and 60 minutes will be evaluated descriptively

- Change from pre-dose in UPDRS Part 3 motor score at 10 to 60 minutes following treatment of patients experiencing an OFF episode.
- Proportion of patients with a ≥ 3 , ≥ 6 , and ≥ 11 -point reduction in the UPDRS Part 3 motor score from pre-dose to post-dose, at 10 to 60 minutes.
- Proportion of patients achieving resolution of an OFF to an ON state within 60 minutes after study drug is administered in the clinic, maintaining the ON state at 60 minutes after study drug administration (per the examiner's subjective assessment).
- Patient-reported total daily OFF time, total daily ON time without dyskinesia, total daily ON time with non-troublesome dyskinesia, and total daily ON time with troublesome dyskinesia, assessed by the patient and recorded in the patient diary.
- Change from baseline visit in the 39-Item Parkinson's Disease Questionnaire (PDQ-39).

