The study includes a screening period of up to 35 days (with 2 screening visits) and a treatment period of approximately 12 months (52 ± 2 weeks) (with 6 treatment/observational visits) plus an additional follow-up at a pulmonary laboratory 4 to 5 weeks after the last treatment/observational visit. A longer screening period may be permitted with approval from the Sponsor. Planned treatment/observational visits will occur at 0 (pre-dose, baseline) and approximately 1, 3, 6, 9, and 12 months. For the CVT-301 treatment group, these visits will be treatment visits and for the observational cohort, these will be observational visits. All patients, regardless of treatment group, will be required to attend all of the screening visits and all of the treatment/observational visits. Assessments for DLco will be performed at a pulmonary laboratory outside of the clinic prior to the TV/OV1, within 2 weeks prior to the 3-, 6-, 9-, and 12-month visits, and 4 to 5 weeks after TV/OV6.

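### DLco is collected in both arms on one schedule, but the between-group model is planned for spirometry only, so DLco gets no planned group difference, confidence interval or baseline adjustment

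*Protocol*

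**What the plan says.** **Objectives (Protocol Section 6).** One secondary objective reads "To describe the effects of CVT-301 on DLco over a 12-month period". Another reads "To estimate the difference between the CVT-301-patients and the observational cohort on measures of pulmonary safety".

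**Role of the cohort (Section 5.2).** The randomised observational cohort "is to permit long-term contemporaneous temporal comparison to CVT-301-treated patients to describe any potential effects of CVT-301 with respect to lung function measurements". The next sentence says that these untreated controls provide what is "required to ascertain the underlying variability in spirometry and DLco endpoints".

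**Data (Sections 7 and 11.1.7).** DLco is measured in both arms at an outside pulmonary laboratory: before TV/OV1, "within 2 weeks prior to the 3-, 6-, 9-, and 12-month visits, and 4 to 5 weeks after TV/OV6".

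**Analysis (Section 12.5, repeated in the synopsis).** DLco is given two descriptive summaries: the change from before to after dosing on the same day, and the change across study days ("For spirometry, DLco, and safety laboratory variables, the differences in pre-dose values between the study days will be described"). The text then says that "the changes in the spirometry values and difference between the groups will be estimated using a Mixed Model for Repeated Measurements (MMRM"). DLco is not named in that sentence. Section 12 adds only that summary statistics are shown by treatment group where applicable.

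**The concern.** A DLco change within the CVT-301 arm mixes any drug effect with ageing, disease progression and drift in laboratory measurement. Only the comparison with the concurrent cohort separates them, and Section 5.2 gives this as the reason for having the cohort. Section 12.5 then fits the group model to one lung-function measure and leaves the other without it. A reader of the results would see two columns of DLco means and would have to judge the difference by eye, without an interval to show how large a loss the data still allow. In a lung-safety trial that upper limit is the useful number.

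**Working it through.** **1. What each part of the protocol provides for the two lung measures.**

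| | Spirometry | DLco |
|---|---|---|
| Measured in both arms on one schedule | Yes | Yes (Sections 7, 11.1.7) |
| Named in the case for the cohort (Section 5.2) | Yes | Yes |
| Change across study days described (Section 12.5) | Yes | Yes |
| Group difference from a repeated-measures model (Section 12.5, synopsis) | Yes | No |
| Confidence interval considered (Section 12.1) | Yes, for FEV1 | No |

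**2. The same-day DLco change.** The time and events tables for the treatment visits (Appendices 4, 6, 8, 10, 12 and 14) ask staff to confirm that a DLco test was done before the visit, to schedule the next one, or both. None has a DLco entry in a post-dose column. Section 12.5 thus plans a summary that has no data. Only the change across study days can be produced, and the term pre-dose has no meaning there for the observational cohort.

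**3. The plan's own figures.** Section 12.1 gives 250 and 115 enrolled with about 25% drop-out: 250 × 0.75 = 187.5 and 115 × 0.75 = 86.25, matching the stated 188 and 86 completers. The FEV1 bound of 0.121 L at 90% power cannot be derived independently because no SD is given. It implies 0.121 / [(1.960 + 1.282) × 0.1302] = 0.287 L, using the standard-error factor from step 4. This concerns FEV1 only and does not affect the DLco point.

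**4. Precision available for DLco from the same patients.** In units of the SD of DLco change:

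- Standard error: √(1/188 + 1/86) = 0.130.
- 95% half-width: 1.96 × 0.130 = 0.255.
- Upper limit not exceeded with 90% power if the true difference is zero: (1.960 + 1.282) × 0.1302 = 0.422.

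The protocol states no SD for DLco change. Assumed SDs of 2, 3, 4 and 5 DLco units give half-widths of 0.51, 0.77, 1.02 and 1.28 units.

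**5. Effect of leaving out patients who were not randomised.** Section 9.2.1 assigns patients from studies 002 and 003 only to CVT-301. Their number is not stated. If 20 or 40 of the 188 completers were such patients (assumptions for illustration):

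- 20: 1.96 × √(1/168 + 1/86) = 0.260.
- 40: 1.96 × √(1/148 + 1/86) = 0.266.

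The loss of precision is small. These figures ignore any gain from baseline adjustment and repeated measures.

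**The case against.** **The objective asks only for description.** It says to describe effects, and descriptive summaries do that. This stands against calling the plan contradictory. It does not remove the point, because Section 5.2 itself ties describing effects to comparison with the cohort.

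**DLco may lie outside the estimation objective.** The objectives that define pulmonary safety do so by spirometry, and the synopsis adds DLco separately under its evaluation criteria. On that reading the objective to estimate a group difference is already met. The text leaves this open, so the point rests on the DLco objective and Section 5.2 instead.

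**Arm summaries and the SAP.** Section 12 allows summaries by group, so an unadjusted comparison is likely. The SAP may add analyses and supersedes the protocol. A reader might infer that DLco gets no controlled comparison at all; the documents do not support that. What is missing from the stated plan is an estimated difference, its interval and the adjustment.

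**Drop-out.** A reader might also infer that observed-case DLco summaries would hide harm because declining patients leave. Simulation with 25% drop-out, visit correlation 0.5 or 0.7 and drop-out depending on the last DLco change shows observed-case means recovering 0.43 to 0.86 of a true 0.3 to 0.5 SD deficit, but only if that dependence exists in the CVT-301 arm alone. With the same mechanism in both arms, the group difference recovers about 0.94 to 1.01. Nothing in the protocol supports the one-sided mechanism, so this bias is not part of the case. Early withdrawers are not wholly lost either: Section 10.3.9 schedules a DLco test 4 to 5 weeks after their withdrawal visit. That test is off treatment, however, and cannot stand in for a 12-month value.

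**Conclusion.** The point holds as a weakly fixed analysis that is almost free to improve. Section 12.5 names DLco, assigns it a summary, and in the next sentence reserves the group model for spirometry, although the cohort is justified for both measures and the data exist in both arms. DLco is left with side-by-side summaries, and one of its two planned summaries has no data behind it. The primary spirometry objective is unaffected.

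The gain is an adjusted 12-month difference with a 95% interval of about ±0.26 SD of DLco change. That size rests on 188 and 86 completers with DLco at 12 months and equal SDs in the two arms. The firm benefits are the interval and the baseline adjustment. A mixed model also gives some protection if drop-out depends on observed DLco.

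**What to change.** In Section 12.5 and the synopsis:

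1. Extend the between-group repeated-measures model to change from baseline in DLco, with group, visit, group-by-visit, baseline DLco and the two stratification factors.
2. Fit it in the randomised patients. Exclude, or present separately, patients from studies 002 and 003 who were assigned directly to CVT-301.
3. Report the 12-month group difference with its 95% confidence interval.
4. Report the DLco test 4 to 5 weeks after visit 6 or early withdrawal as a separate off-treatment time point, not pooled with the on-treatment visits.
5. Remove DLco from the sentence on same-day change around dosing, and use wording for the change across study days that also applies to the observational cohort.

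The cost is a few phrases in the protocol, matching text in the SAP and one more model output. No new assessments or patients are needed.
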